12 OCT 2020

## SYNOPSIS

### Protocol Title

A Randomized Open-Label, Phase 1b Study of the Safety of Pirfenidone Solution for Inhalation (AP01) in Patients with Idiopathic Pulmonary Fibrosis (ATLAS Study)

### Protocol Number

AP01-002

### Clinical Phase

Phase 1b

### Product Sponsor

Avalyn Pharma, Inc.

### Indication

Idiopathic Pulmonary Fibrosis (IPF)

### Investigational Drug

Pirfenidone Solution for Inhalation (AP01)

### Control

None (Open-label)

### Objectives

To evaluate the safety and tolerability of AP01 given once or twice daily to patients with IPF.

To estimate the treatment effect of AP01 given 50 milligrams (mg) once daily and 100 mg twice daily on the absolute change in percent of predicted forced vital capacity (% FVC) in patients with IPF.

### Safety Outcome Measures

- Treatment-emergent adverse events (AEs)
- Change from pre-dose to post-dose FEV1 after initial dose
- Treatment-emergent deaths
- Treatment-emergent changes in clinical laboratory findings
- Changes in vital signs

Avalyn Pharma, Inc.  
AP01-002

Protocol v2.1  
12 OCT 2020

## Efficacy Outcome Measures

- Change from Baseline in % FVC
- Change from Baseline in diffusing capacity of the lungs for carbon monoxide ( $D_{LCO}$ )
- Change from Baseline in Patient Reported Outcomes (PROs) scores
- Change from Baseline in cough frequency and intensity
- Change from Baseline in the extent of fibrosis and lung volumes as measured by High Resolution Computed Tomography (HRCT)

## Exploratory Endpoints

- Correlation between weekly home spirometry measurements and in-clinic spirometry values
- Correlation of extent of fibrosis and lung volumes as measured by HRCT at Baseline and Week 24 to other measures of clinical status, e.g. spirometry
- Change from Baseline in serum biomarkers of alveolar epithelial injury (CA19-9 and CA-125)

## Investigational Products

### Investigational Drug Dosage

50 mg AP01, 100 mg AP01

### Number of Patients

Approximately 100 patients will be treated; 50 each with 50 mg once daily or 100 mg twice daily

## Study Duration

This study has two parts. In Part A, each patient will be screened and those enrolled will then receive 24 weeks treatment with AP01. Patients that complete Part A and in the opinion of the investigator are compliant with study procedures will be allowed to continue to Part B of the study for 48 weeks additional treatment.

If patients discontinue study treatment prior to Week 72 for any reason, they should return to the site for an Early Termination visit. All patients who complete the regular study visits through Part B will return for a Follow-up visit 28 days after their End of Study visit (EOS/Visit 12) unless the patient has consented to enroll in the Rollover study, AP01-005.

The end of study for patients that plan to participate in the Rollover study (AP01-005) will be their last treatment visit (EOS/Visit 12) or an safety monitoring visit after Visit 12. The end of the study for patients not enrolling in AP01-005 will be the day of their last Follow-up or Early Termination visit.

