12 OCT 2020

### **3. STUDY ENDPOINTS**

#### **3.1. Safety Outcome Measures**

- Treatment-emergent AEs
- Change from pre-dose to post-dose FEV1 after initial dose
- Treatment-emergent deaths
- Treatment-emergent changes in clinical laboratory findings
- Changes in vital signs

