#### **5.6. Patient Withdrawal Criteria**

Patient participation in the study is purely voluntary; patients can withdraw consent at any time for any reason without effect on subsequent care. This is an open-label study in which the investigator is aware of the patient's treatment assignment. The investigator, in consultation with the Medical Monitor, or the Medical Monitor may exercise his or her medical judgment to terminate a patient's participation in the study due to clinically significant changes in any clinical or laboratory parameter. If in the opinion of the investigator, the patient is failing the study drug for lack of efficacy, as evidenced by an excessive decline of FVC, during Part A of the study, the patient can be withdrawn and placed on alternative therapies. During Part B of the study, the investigator may choose to add nintedanib, but not oral pirfenidone, to the patient's treatment regimen.

Any randomized patient desiring to discontinue prior to study completion should be encouraged to discuss his or her reasons and concerns with the investigator. If, after discussion, the patient still chooses to discontinue participation in the study, the patient should be encouraged to attend an Early Termination visit. (Patients that discontinue during the screening process will be considered screen failures.) Patients who are discontinued during a scheduled visit will be encouraged to complete all unique assessments for both that study visit and the End of Treatment visit at the time of discontinuation. If a patient is still participating in Part A and has had a HRCT scan within the past month, the HRCT from the End of Treatment visit will not be performed.

An End of Study case report form (CRF) page will be completed for every patient who receives study medication whether or not the patient completes the study. The reason for any early discontinuation from the study will be indicated on this form. The primary reason for any early termination will be selected from the following standard categories:

- Adverse Event: Clinical or laboratory events occurred that in the medical judgment of the investigator, in consultation with the Medical Monitor and Avalyn Pharma, represents an unacceptable risk to the patient if he/she continues in the study. This includes serious and non-serious AEs regardless of relationship to study medication. The investigator must follow the patient until the AE resolves or satisfactorily stabilizes

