#### **6.2.11 Follow-up Visit for Patients NOT Enrolling in AP01-005 (28 days +/- 7 days after the Visit 12 - End of Study visit)**

Follow-up visits will occur 28 days after the End of Study visit for Part B. The following procedures will be conducted in chronological order:

- Cough VAS, KBILD Questionnaire and LCQ
- AEs and concomitant medications since previous visit
- Modified PE (Lungs and CV body systems only)
- Vital signs
- SaO2
- Spirometry and DLCO
- Blood samples for laboratory tests (Chemistry including AST and ALT, Hematology, Biomarkers (CA19-9 and CA-125 only))
- Urinalysis
- End of Study form completion

Patients may experience AEs that necessitate an unscheduled visit. There may also be situations in which the investigator asks a patient to report for an unscheduled visit following the report of an AE or a significant decrease in FVC during home spirometry readings. Additional examinations may be conducted at these visits as necessary to ensure the safety and well-being of patients during the study. Electronic case report forms (eCRFs) should be completed for each unscheduled visit.

Avalyn Pharma, Inc.  
AP01-002

Protocol V2.1  

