**Notes for Tables 5 and 6:**

1. Follow-up visit will occur 28 days after the End of Study visit in Part B of the study.
2. A complete physical exam will be performed at Screening and Baseline visits. A modified physical exam including the patient's lungs and cardiovascular body systems will be performed at all other visits. For Safety Visits, only chest and skin exam are required.
3. Height is collected at the Screening visit only.
4. Blood samples for laboratory tests include: Chemistry (including AST and ALT), Hematology and Biomarkers (Blood samples for biomarkers will not be collected at Screening.) For Safety Visits, only AST and ALT are required.
5. Females of childbearing potential are required to take a urinary pregnancy test at each visit except the Follow-up visit.
6. Patients that pass screening and are scheduled to be randomized will receive a LCM to be worn for 24 hours and returned to the site at the Baseline visit. LCM will be worn for 24 hours at Visits 5 and 8. A paper diary will also be dispensed to the patient to record activities during the 24-hour period.
7. HRCT scans will be performed at Visits 2 and 8. The Baseline HRCT may be skipped if the HRCT for eligibility was performed less than 1 month prior to the Baseline visit.
8. Study material dispensation will occur at Visit 8 for those patients participating in Part B of the study.
9. Patients will be assessed for eligibility to participate in AP01-005 at EOS/Visit 12. Those enrolling in AP01-005 will use EOS/Visit 12 as their AP01-005 Baseline visit.
10. Patients enrolling in AP01-005 will not participate in the Follow-up visit.
11. Patients awaiting site approval of AP01-005 only.

Avalyn Pharma, Inc.  
AP01-002

Protocol V2.1  

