### **7.4.1. Adverse Events**

All AEs will be collected from informed consent through the Follow-up visit. Details regarding AE definitions, collection, recording, and reporting are found in Section 10.1.

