### **10.1.4 Collecting and Recording AEs**

#### **10.1.4.1 Period of Collection**

All AEs will be collected from the time of informed consent through the final study visit. All AEs and SAEs should be treated as medically appropriate and followed until event resolution.

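### Patients who leave early have no contact for new adverse events or deaths after the Early Termination visit, so off-drug safety observation depends on how a patient exits

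*Protocol*

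**What the plan says.** The Protocol Synopsis (Study Duration) states: "All patients who complete the regular study visits through Part B will return for a Follow-up visit 28 days after their End of Study visit", with an exception for those who have consented to the rollover study AP01-005. Section 6.2.11 sets the anchor: "Follow-up visits will occur 28 days after the End of Study visit for Part B", with a window of +/- 7 days. The notes to Tables 5 and 6 add: "Patients enrolling in AP01-005 will not participate in the Follow-up visit". Those patients continue AP01.

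Patients who stop treatment before Week 72 (Synopsis; Section 4.1), and those who do not go on to Part B (Synopsis, Study Overview/Design), are to attend an Early Termination visit. No interval from last dose is given for it, and it has no column in Table 5 or Table 6. Under Section 5.6, a patient discontinued during a scheduled visit is encouraged to do the end-of-treatment assessments then and there. The study closes for these patients at that visit: "The end of the study for patients not enrolling in AP01-005 will be the day of their last Follow-up or Early Termination visit".

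The end of AE collection is stated twice. Section 7.4.1 says: "All AEs will be collected from informed consent through the Follow-up visit". Section 10.1.4.1 says: "All AEs will be collected from the time of informed consent through the final study visit".

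Section 3.1 lists treatment-emergent AEs and "Treatment-emergent deaths" among the safety outcomes, and safety is the primary objective (Section 4.1).

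**The concern.** Leavers are not a random subset. Section 5.6 lists AEs and lack of tolerability as reasons for leaving. It also says of a Part A patient with excessive FVC decline that "the patient can be withdrawn and placed on alternative therapies". Sections 4.1, 5.3 and 8.9.1 direct that a Part A patient who needs oral pirfenidone or nintedanib be discontinued from the study.

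Such a patient may have no planned observation for new events after the last dose, while a non-rollover completer has about four weeks. The observed rate of off-drug AEs and deaths then depends partly on exit route. If the two regimens lose patients at different rates, the comparison of their safety, a stated objective in Section 2, is affected too.

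There is also an efficacy consequence. In the sensitivity analyses of SAP 8.1, visits missing because of death are set to an FVC of 30% predicted. Visits missing after other early termination take the average change of the patient's cohort. A Part A leaver who dies before Week 24 without the study learning of it falls under the second rule.

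**Working it through.** **The plan's own figure.** Table 10 gives the chance of seeing at least one event among 50 patients. With 1 - (1 - p)^50 the results are 0.395 (p = 1%), 0.923 (5%) and 0.995 (10%). All three reproduce, and this point does not dispute them.

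**Exit routes side by side.**

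| Exit route | Last planned AP01-002 contact | Planned off-drug window for new events |
|---|---|---|
| Completes Part B, no rollover | Follow-up visit | 28 (+/- 7) days after Visit 12 |
| Completes Part B, rolls over | Visit 12 or a later safety visit | Not applicable; stays on AP01 |
| Stops before Week 72 | Early Termination visit | Not fixed; zero if done on the day of stopping |
| Finishes Part A, no Part B | Early Termination visit | Not fixed; can be zero |

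**Does another section close the gap?**
- Section 7.4.1 runs AE collection to a visit that the last two groups do not have. Section 10.1.4.1 runs it to the final study visit, which for them is Early Termination. Neither rule reaches beyond that visit.
- Section 10.1.1.2 requires reporting of deaths during the study, or learned of in a protocol-defined follow-up period. No such period is defined after Early Termination.
- Sections 5.6, 10.1.4.1 and 10.1.4.3.1 require follow-up of events already present. They do not set a contact to find new ones.

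**Illustrative size.** The documents give neither a dropout rate for this trial nor a post-exit event rate. I assume n = 10, 20 or 30 leavers out of 100, and a risk r of 2% or 5% of a new event in the 28 days after the Early Termination visit. Expected events are n x r. The chance of at least one is 1 - (1 - r)^n.

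| n | r = 2% | r = 5% |
|---|---|---|
| 10 | 0.2 expected; chance 0.18 | 0.5; 0.40 |
| 20 | 0.4; 0.33 | 1.0; 0.64 |
| 30 | 0.6; 0.45 | 1.5; 0.79 |

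At most 10 x 28 = 280 to 30 x 28 = 840 patient-days go unobserved, against 100 x 504 = 50,400 planned, or 0.6% to 1.7%. The true loss is smaller wherever the Early Termination visit falls some days after the last dose.

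**Imputation, per unrecorded death.** The eligible FVC range at Screening is 40% to 90% predicted. Take this as the baseline range. The death rule then gives a change of 30 - 40 = -10 to 30 - 90 = -60 points. Suppose the cohort average change is -1.5, the oral pirfenidone figure in Table 11. The two rules then differ by 8.5 to 58.5 points for that patient. Divided by 50 patients, the arm's simple mean change at Week 24 moves by 0.17 to 1.17 points. The planned 95% CI half-width is 1.25. The effect on a fitted slope would differ, and only the sensitivity analyses are touched.

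**The case against.** The strongest reply is that the patients at highest risk are already covered. AEs that lead to discontinuation are followed until resolved or stable (Section 5.6). SAEs are followed, whatever their relationship to drug, until they resolve, stabilise or become non-serious (Section 10.1.4.3.1). A death that is the outcome of an SAE open at exit should therefore be captured. This stands. A reader might infer that nothing is collected after early stopping, and the documents do not say that. The gap is new-onset events.

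Other stronger readings also go too far:
- **Every leaver has a zero-day window.** Same-day assessment is described only for patients discontinued at a scheduled visit. For the rest, the interval is unspecified.
- **The Follow-up visit goes to the healthiest patients.** It goes to completers who stop AP01. Completers may choose rollover, and nothing shows that those who do not are healthier.
- **The SAP presumes data that are not collected.** A TEAE definition without an end date (SAP 10.1) counts whatever is recorded. The 30-day rule in SAP 7.6 classifies recorded medications, and 30 days also exceeds the nominal 28 days for completers.
- **A death will be missed.** A 5% risk per 28 days, read as mortality, is about 49% a year (1 - 0.95^13). Protocol 1.1 gives survival of roughly 2 to 5 years. Taken as a median with constant hazard (an assumption), that is 1.1% to 2.6% per 28 days, or 0.2 to 0.5 deaths in 20 leavers, before removing deaths from SAEs already open. Leavers may be at higher risk, but the documents do not say by how much.

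Two further replies have some weight. After the amendment all Part B patients receive one regimen, and nintedanib may be added in Part B, so any distortion between regimens arises mainly in Part A. And with an oral half-life of about 2.4 hours and low systemic exposure after inhalation, many late events would reflect the disease or new therapy. That limits causal reading of these events, but it does not justify observing them differently by exit route.

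**Conclusion.** The gap is real and structural. For non-rollover patients, systematic collection of new AEs, SAEs and deaths after stopping AP01 depends on exit route, and nothing elsewhere in the Protocol or SAP corrects this. Sections 7.4.1 and 10.1.4.1 also state the end of AE collection differently and need reconciling.

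Confidence is high in the structure and low in the size. The range of 0.2 to 1.5 expected uncollected events rests wholly on assumed numbers of leavers (10 to 30) and an assumed 28-day risk (2% to 5%). Bias between regimens is possible only if they differ in early exits, mainly in Part A, and the documents do not show that they do. The imputation effect needs a leaver to die unrecorded before Week 24, and it reaches only the sensitivity analyses. This is a cheap improvement, not a defect that invalidates the safety analysis.

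**What to change.** - **Protocol 4.1, 5.6 and 6.2:** for every patient who stops AP01, does not enter AP01-005 and would not otherwise have the Follow-up visit, add a telephone contact 28 (+/- 7) days after last dose. Record new AEs and SAEs, new IPF therapy and vital status, unless consent is withdrawn. For patients who left Part A early, also record vital status at Week 24.
- **Protocol 7.4.1 and 10.1.4.1:** state one rule. AEs are collected through that contact or the Follow-up visit for non-rollover patients, and through the last AP01-002 visit for rollover patients.
- **SAP 10.1:** use one post-dose TEAE window for all non-rollover patients, long enough to hold the visit allowance, for example 28 + 7 = 35 days after last dose. A hard 28-day limit would drop events found at Follow-up visits on days 29 to 35. Flag events that start after a new antifibrotic, and align the 30-day window in SAP 7.6 so that such starts are counted.
- **SAP 8.1:** say that a death known to have occurred after early termination and before Week 24 takes the death rule from the date of death.

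The cost is one call per leaver, of a kind sites already make at Week 1 and monthly in Part B, plus short amendments. Some events will be confounded by new therapy, and reported AE and death counts may rise slightly.

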## Study Population

- Male and female patients at least 40 years of age

Avalyn Pharma, Inc.  
AP01-002

Protocol v2.1  
12 OCT 2020

- $40\% \leq \text{FVC} \leq 90\%$  predicted; The first 20 patients randomized must have  $\text{FVC} \geq 50\%$  predicted. After the first 20 patients have been randomized, patients with  $\text{FVC} 40\% < 50\%$  predicted will be allowed to be randomized in the study but randomization for these patients will be capped at 20.
- $\text{FEV}_1/\text{FVC}$  ratio  $\geq 70\%$
- Not eligible for oral pirfenidone and nintedanib due to national formulary restrictions OR intolerant to or unwilling to start oral pirfenidone and nintedanib, if previously offered (Nintedanib use is allowed in Part B of the study)
- Confident diagnosis of IPF based on clinical, radiologic and pathologic data without evidence or suspicion of an alternative diagnosis that may contribute to their interstitial lung disease
- $30 \leq \% \text{D}_{\text{LCO}} \leq 90\%$

## Study Overview/Design

This is a randomized, open-label study of Pirfenidone Solution for Inhalation (AP01) 50 mg once daily or 100 mg twice daily. This study has 2 parts.

Part A (24 weeks): Patients will be randomized in a 1:1 ratio to one of two treatment arms: 50 mg once daily or 100 mg twice daily. On Day 1, the initial dose of the drug will be administered in the clinic to confirm airway tolerance. If in the investigator's opinion, the patient had tolerability issues during the first dose administration, a second dose, at least 4 hours later, will also be observed. The remainder of the doses will be administered by the patient outside of the clinic. Patients will have a telephone assessment at Week 1 and an in-clinic assessment at Weeks 4, 8, 12, 16, 20, and 24. Patients who do not continue to Part B or who are withdrawn from the study prior to completion should return for an Early Termination visit. Week 4 safety data from the first 20 patients will be reviewed by a Data and Safety Monitoring Board (DSMB), who may suggest changes to design or stopping of the study based on safety concerns.

Part B (48 weeks): Patients who, in the opinion of the investigator, are compliant with study treatment dosing and study procedures will be permitted to enter Part B. All patients continuing to Part B prior to the implementation of this amendment will continue to receive the treatment regimen (50 mg once daily or 100 mg twice daily) to which they were randomized in Part A. If one dosing regimen is determined to be superior either from an efficacy or safety standpoint, Part B may be converted to a single dose regimen.

The DSMB for this study met on 12 OCT 2020 to review preliminary dose comparison data. It was determined that the 100 mg twice daily dose showed a trend for amelioration of FVC loss and recommended all patients in Part B be treated with the 100 mg twice daily dose. Therefore, all patients who participate in Part B after the implementation of this amendment will be treated with the 100 mg twice daily dose. Any patients already participating in Part B on the 50 mg once daily dose will be converted to the 100 mg twice daily dose regimen. Patients will have monthly telephone assessments and quarterly in-clinic assessments. All patients that complete the study visits through Part B will have the option to continue receiving AP01 by enrolling or planning to enroll in the AP01-005 study or to stop dosing after the EOS/Visit 12 and return for a Follow-up visit, 28 days after their End of Study visit.

## Statistics

### Power and Sample Size

Avalyn Pharma, Inc.  
AP01-002

Protocol v2.1  
12 OCT 2020

This is an open-label study; no formal hypothesis testing is planned. 50 patients per arm will be adequate to assess the safety and tolerability of AP01 given once or twice daily, as well as provide estimation of changes in response endpoints over time.

### **Primary Analysis**

Safety and tolerability will be assessed by treatment emergent AE rates, post-first dose spirometry, deaths, clinically significant laboratory findings and vital signs.

### **Secondary Analyses**

Change from baseline in FVC % predicted,  $D_{LCO}$ , PRO domain scores, cough frequency, extent of fibrosis and lung volumes over 24 and 72 weeks will be analyzed by treatment arm.

Avalyn Pharma, Inc.  
AP01-002

Protocol v2.1  

12 OCT 2020

Avalyn Pharma, Inc.  
AP01-002

Protocol v2.1  

12 OCT 2020

## LIST OF ABBREVIATIONS

The following abbreviations are used in this study protocol.

6MWT	6-Minute Walk Test
ADR	Adverse Drug Reaction
AE	Adverse Event
ALT	Alanine Aminotransferase
ADL	Activities of Daily Living
AP01	Pirfenidone Solution for Inhalation
AST	Aspartate Aminotransferase
ATS	American Thoracic Society
AUC	Area Under the Concentration-Time Curve
AUC (0-x)	Area Under the Concentration-Time Curve from Time 0 to x Hours Post Dose
BAL	Bronchoalveolar Lavage
BFS	Blow-Fill-Seal
C max	Maximum Concentration
CE	Conformité Européene
CFR	Code of Federal Regulations
CI	Confidence Interval
CRF	Case Report Form
CRO	Contract Research Organization
CV	Cardiovascular
CYP	Cytochrome P450 Family
CYP1A2	Cytochrome P450 Family Subfamily A Member 2
DSMB	Data and Safety Monitoring Board
D LCO	Diffusion Capacity for Carbon Monoxide
EC	Ethics Committee
EC 50	Half Maximal Effective Concentration
ECG	Electrocardiogram
eCRF	Electronic Case Report Form
eFlow	eFlow ® Nebulizer System
ELF	Epithelial Lining Fluid
EOS	End of Study
ERS	European Respiratory Society
FEV 1	Forced Expiratory Volume in One Second
FOCBP	Female of Child-Bearing Potential
FVC	Forced Vital Capacity
GCP	Good Clinical Practice
GLP	Good Laboratory Practice
GMP	Good Manufacturing Practice
GSD	Geometric Standard Deviation
HRCT	High-Resolution Computed Tomography
IB	Investigator's Brochure
ICH	International Conference on Harmonisation
IP	Investigational Product
IPF	Idiopathic Pulmonary Fibrosis
IRB	Institutional Review Board
KBILD	The King's Brief Interstitial Lung Disease
Kg	Kilogram
L	Liters

Avalyn Pharma, Inc.  
AP01-002

Protocol v2.1  
